Table 119: Number and Percentage of Subjects Experiencing Solicited Systemic Events by Symptom, Severity, Week, and Treatment Group - Safety Population - All Subjects - Weeks 1-6

Treatment Group= All (N=X)													
Solicited Adverse Event	Severity ¹	Week 1 (N=X)		Week 2 (N=X)		Week 3 (N=X)		Week 4 (N=X)		Week 5 (N=X)		Week 6 (N=X)	
		n	%	n	%	n	%	n	%	n	%	n	%
Any Solicited Systemic Event	None	x	x	x	x	x	x	x	x	x	x	x	x
	Mild	x	x	x	x	x	x	x	x	x	x	x	x
	Moderate	x	x	x	x	x	x	x	x	x	x	x	x
	Severe	x	x	x	x	x	x	x	x	x	x	x	x
Nausea*	None	x	x	x	x	x	x	x	x	x	x	x	x
	Mild	x	x	x	x	x	x	x	x	x	x	x	x
	Moderate	x	x	x	x	x	x	x	x	x	x	x	x
	Severe	x	x	x	x	x	x	x	x	x	x	x	x
Vomiting*	None	x	x	x	x	x	x	x	x	x	x	x	x
	Mild	x	x	x	x	x	x	x	x	x	x	x	x
	Moderate	x	x	x	x	x	x	x	x	x	x	x	x
	Severe	x	x	x	x	x	x	x	x	x	x	x	x
Abdominal pain/cramps*	None	x	x	x	x	x	x	x	x	x	x	x	x
	Mild	x	x	x	x	x	x	x	x	x	x	x	x
	Moderate	x	x	x	x	x	x	x	x	x	x	x	x
	Severe	x	x	x	x	x	x	x	x	x	x	x	x
Diarrhea*	None	x	x	x	x	x	x	x	x	x	x	x	x
	Mild	x	x	x	x	x	x	x	x	x	x	x	x
	Moderate	x	x	x	x	x	x	x	x	x	x	x	x
	Severe	x	x	x	x	x	x	x	x	x	x	x	x

Treatment Group= All (N=X)													
		Week 1 (N=X)		Week 2 (N=X)		Week 3 (N=X)		Week 4 (N=X)		Week 5 (N=X)		Week 6 (N=X)	
Solicited Adverse Event	Severity ¹	n	%	n	%	n	%	n	%	n	%	n	%
Constipation*	None	x	x	x	x	x	x	x	x	x	x	x	x
	Mild	x	x	x	x	x	x	x	x	x	x	x	x
	Moderate	x	x	x	x	x	x	x	x	x	x	x	x
	Severe	x	x	x	x	x	x	x	x	x	x	x	x
Pain/burning with urination	None	x	x	x	x	x	x	x	x	x	x	x	x
	Mild	x	x	x	x	x	x	x	x	x	x	x	x
	Moderate	x	x	x	x	x	x	x	x	x	x	x	x
	Severe	x	x	x	x	x	x	x	x	x	x	x	x
Frequent urination	None	x	x	x	x	x	x	x	x	x	x	x	x
	Mild	x	x	x	x	x	x	x	x	x	x	x	x
	Moderate	x	x	x	x	x	x	x	x	x	x	x	x
	Severe	x	x	x	x	x	x	x	x	x	x	x	x
Blood in urine*	None	x	x	x	x	x	x	x	x	x	x	x	x
	Mild	x	x	x	x	x	x	x	x	x	x	x	x
	Moderate	x	x	x	x	x	x	x	x	x	x	x	x
	Severe	x	x	x	x	x	x	x	x	x	x	x	x
Headache*	None	x	x	x	x	x	x	x	x	x	x	x	x
	Mild	x	x	x	x	x	x	x	x	x	x	x	x
	Moderate	x	x	x	x	x	x	x	x	x	x	x	x
	Severe	x	x	x	x	x	x	x	x	x	x	x	x

Notes: Denominator for percentages is the number of subjects in the Safety Population (N) completing memory aid that week.
 *Symptom not collected during weeks 12-24.
¹The maximum severity of any solicited adverse event is summarized. A subject is only counted once at the maximum severity.

Table 120: Number and Percentage of Subjects Experiencing Solicited Systemic Events by Symptom, Severity, Week, and Treatment Group—Safety Population—All Subjects—Weeks 7-24

Treatment Group=All (N=X)															
Solicited Adverse Event	Severity ¹	Week 7 (N=X)		Week 8 (N=X)		Week 9 (N=X)		Week 10 (N=X)		Week 11 (N=X)		Weeks 12-18 (N=X)		Weeks 19-24 (N=X)	
		n	%	n	%	n	%	n	%	n	%	n	%	n	%
Any Solicited Systemic Event	None	x	x	x	x	x	x	x	x	x	x	x	x	x	x
	Mild	x	x	x	x	x	x	x	x	x	x	x	x	x	x
	Moderate	x	x	x	x	x	x	x	x	x	x	x	x	x	x
	Severe	x	x	x	x	x	x	x	x	x	x	x	x	x	x
Nausea*	None	x	x	x	x	x	x	x	x	x	x	-	-	-	-
	Mild	x	x	x	x	x	x	x	x	x	x	-	-	-	-
	Moderate	x	x	x	x	x	x	x	x	x	x	-	-	-	-
	Severe	x	x	x	x	x	x	x	x	x	x	-	-	-	-
Vomiting*	None	x	x	x	x	x	x	x	x	x	x	-	-	-	-
	Mild	x	x	x	x	x	x	x	x	x	x	-	-	-	-
	Moderate	x	x	x	x	x	x	x	x	x	x	-	-	-	-
	Severe	x	x	x	x	x	x	x	x	x	x	-	-	-	-
Abdominal pain/cramps*	None	x	x	x	x	x	x	x	x	x	x	-	-	-	-
	Mild	x	x	x	x	x	x	x	x	x	x	-	-	-	-
	Moderate	x	x	x	x	x	x	x	x	x	x	-	-	-	-
	Severe	x	x	x	x	x	x	x	x	x	x	-	-	-	-
Diarrhea*	None	x	x	x	x	x	x	x	x	x	x	-	-	-	-
	Mild	x	x	x	x	x	x	x	x	x	x	-	-	-	-
	Moderate	x	x	x	x	x	x	x	x	x	x	-	-	-	-
	Severe	x	x	x	x	x	x	x	x	x	x	-	-	-	-

Treatment Group=All (N=X)															
		Week 7 (N=X)		Week 8 (N=X)		Week 9 (N=X)		Week 10 (N=X)		Week 11 (N=X)		Weeks 12-18 (N=X)		Weeks 19-24 (N=X)	
Solicited Adverse Event	Severity ¹	n	%	n	%	n	%	n	%	n	%	n	%	n	%
Constipation*	None	x	x	x	x	x	x	x	x	x	x	-	-	-	-
	Mild	x	x	x	x	x	x	x	x	x	x	-	-	-	-
	Moderate	x	x	x	x	x	x	x	x	x	x	-	-	-	-
	Severe	x	x	x	x	x	x	x	x	x	x	-	-	-	-
Pain/burning with urination	None	x	x	x	x	x	x	x	x	x	x	x	x	x	x
	Mild	x	x	x	x	x	x	x	x	x	x	x	x	x	x
	Moderate	x	x	x	x	x	x	x	x	x	x	x	x	x	x
	Severe	x	x	x	x	x	x	x	x	x	x	x	x	x	x
Frequent urination	None	x	x	x	x	x	x	x	x	x	x	x	x	x	x
	Mild	x	x	x	x	x	x	x	x	x	x	x	x	x	x
	Moderate	x	x	x	x	x	x	x	x	x	x	x	x	x	x
	Severe	x	x	x	x	x	x	x	x	x	x	x	x	x	x
Blood in urine*	None	x	x	x	x	x	x	x	x	x	x	-	-	-	-
	Mild	x	x	x	x	x	x	x	x	x	x	-	-	-	-
	Moderate	x	x	x	x	x	x	x	x	x	x	-	-	-	-
	Severe	x	x	x	x	x	x	x	x	x	x	-	-	-	-
Headache*	None	x	x	x	x	x	x	x	x	x	x	-	-	-	-
	Mild	x	x	x	x	x	x	x	x	x	x	-	-	-	-
	Moderate	x	x	x	x	x	x	x	x	x	x	-	-	-	-
	Severe	x	x	x	x	x	x	x	x	x	x	-	-	-	-

Notes: Denominator for percentages is the number of subjects in the Safety Population (N) completing memory aid that week.
 *Symptom not collected during weeks 12-24.
¹The maximum severity of any solicited adverse event is summarized. A subject is only counted once at the maximum severity.

Tables with Similar Format:

Table 121: Number and Percentage of Subjects Experiencing Solicited Local Events by Symptom, Severity, Week, and Treatment Group—Safety Population—LACTIN-V—Weeks 1-6

Table 122: Number and Percentage of Subjects Experiencing Solicited Local Events by Symptom, Severity, Week, and Treatment Group—Safety Population—LACTIN-V—Weeks 7-24

Table 123: Number and Percentage of Subjects Experiencing Solicited Local Events by Symptom, Severity, Week, and Treatment Group—Safety Population—Placebo—Weeks 1-6

Table 124: Number and Percentage of Subjects Experiencing Solicited Local Events by Symptom, Severity, Week, and Treatment Group—Safety Population—Placebo—Weeks 7-24

Table 125: Proportion of Subjects Reporting Product Related Unsolicited Adverse Events Following the First Dose of Study Product through Visit 7 by Treatment Group – Safety Population

Treatment Group	Number of Subjects with AEs n	Number of Subjects N	Proportion of Subjects with AEs	Proportion of Subjects with AEs 95% CI	Difference in Proportion of Subjects with AEs between LACTIN-V and Placebo	Difference in Proportion of Subjects with AEs between LACTIN-V and Placebo 95% CI	P-value*
LACTIN-V	x	x	0.xx	0.xx, 0.xx	0.xx	0.xx, 0.xx	0.xxx
Placebo	x	x	0.xx	0.xx, 0.xx	--	--	--
All Subjects	x	x	0.xx	0.xx, 0.xx	--	--	--

Notes: The denominator for proportions is based on the number of subjects enrolled in the respective treatment group and analysis population.

*P-value from the Fisher’s exact two-sided test at the .05 level of significance.

95% CI= 95% Blaker Confidence Interval

Table 126: Number and Percentage of Subjects Experiencing Unsolicited Adverse Events with 95% Confidence Intervals by MedDRA System Organ Class and Preferred Term, Dose Number, and Treatment Group - Safety Population

MedDRA System Organ Class	MedDRA Preferred Term	LACTIN-V (N=X)			Placebo (N=X)			All Subjects (N=X)		
		n	%	95% CI	n	%	95% CI	n	%	95% CI
Any SOC	Any PT	x	x	x, x	x	x	x, x	x	x	x, x
[SOC 1]	Any PT	x	x	x, x	x	x	x, x	x	x	x, x
	[PT 1]	x	x	x, x	x	x	x, x	x	x	x, x
	[PT 2]	x	x	x, x	x	x	x, x	x	x	x, x
[SOC 2]	Any PT	x	x	x, x	x	x	x, x	x	x	x, x
	[PT 1]	x	x	x, x	x	x	x, x	x	x	x, x
	[PT 2]	x	x	x, x	x	x	x, x	x	x	x, x

Notes: N = number of subjects in the Safety Analysis Population who received the specified treatment.

This table presents number and percentage of subjects.

A subject is only counted once per PT/timepoint.

95% CI= 95% Blaker Confidence Interval

Table 127: Number and Percentage of Subjects Experiencing Unsolicited Adverse Events by MedDRA System Organ Class and Preferred Term, Maximum Severity and Relationship—Safety Population

			All Subjects (N = X)								
			Related			Not Related			Total		
			n	%	Freq	n	%	Freq	n	%	Freq
Any SOC	Any PT	Any Severity	x	x.X	x	x.X	x	x.X	x	x.X	x
		Mild	x	x.X	x	x.X	x	x.X	x	x.X	x
		Moderate	x	x.X	x	x.X	x	x.X	x	x.X	x
		Severe	x	x.X	x	x.X	x	x.X	x	x.X	x
[SOC 1]	Any PT	Any Severity	x	x.X	x	x.X	x	x.X	x	x.X	x
		Mild	x	x.X	x	x.X	x	x.X	x	x.X	x
		Moderate	x	x.X	x	x.X	x	x.X	x	x.X	x
		Severe	x	x.X	x	x.X	x	x.X	x	x.X	x
	[PT 1]	Any Severity	x	x.X	x	x.X	x	x.X	x	x.X	x
		Mild	x	x.X	x	x.X	x	x.X	x	x.X	x
		Moderate	x	x.X	x	x.X	x	x.X	x	x.X	x
		Severe	x	x.X	x	x.X	x	x.X	x	x.X	x

Notes: N = Number of subjects in the Safety Analysis Population
 This table presents number and percentage of subjects as well as number of events.
 For severity, a subject is counted once per preferred term and is summarized according to their highest severity.

Table 128: Number and Percentage of Subjects Experiencing Unsolicited Adverse Events by MedDRA System Organ Class and Preferred Term, Maximum Severity, Relationship, and Treatment Group - Safety Population

			LACTIN-V (N = X)									Placebo (N = X)								
			Related			Not Related			Total			Related			Not Related			Total		
			n	%	Freq	n	%	Freq	n	%	Freq	n	%	Freq	n	%	Freq	n	%	Freq
Any SOC	Any PT	Any Severity	x	x.x	x	x.x	x	x.x	x	x.x	x	x.x	x	x.x	x	x.x	x	x.x	x	x.x
		Mild	x	x.x	x	x.x	x	x.x	x	x.x	x	x.x	x	x.x	x	x.x	x	x.x	x	x.x
		Moderate	x	x.x	x	x.x	x	x.x	x	x.x	x	x.x	x	x.x	x	x.x	x	x.x	x	x.x
		Severe	x	x.x	x	x.x	x	x.x	x	x.x	x	x.x	x	x.x	x	x.x	x	x.x	x	x.x
[SOC 1]	Any PT	Any Severity	x	x.x	x	x.x	x	x.x	x	x.x	x	x.x	x	x.x	x	x.x	x	x.x	x	x.x
		Mild	x	x.x	x	x.x	x	x.x	x	x.x	x	x.x	x	x.x	x	x.x	x	x.x	x	x.x
		Moderate	x	x.x	x	x.x	x	x.x	x	x.x	x	x.x	x	x.x	x	x.x	x	x.x	x	x.x
		Severe	x	x.x	x	x.x	x	x.x	x	x.x	x	x.x	x	x.x	x	x.x	x	x.x	x	x.x
	[PT 1]	Any Severity	x	x.x	x	x.x	x	x.x	x	x.x	x	x.x	x	x.x	x	x.x	x	x.x	x	x.x
		Mild	x	x.x	x	x.x	x	x.x	x	x.x	x	x.x	x	x.x	x	x.x	x	x.x	x	x.x
		Moderate	x	x.x	x	x.x	x	x.x	x	x.x	x	x.x	x	x.x	x	x.x	x	x.x	x	x.x
		Severe	x	x.x	x	x.x	x	x.x	x	x.x	x	x.x	x	x.x	x	x.x	x	x.x	x	x.x

Notes: N = Number of subjects in the Safety Analysis Population
 This table presents number and percentage of subjects as well as number of events.
 For severity, a subject is counted once per preferred term and is summarized according to their highest severity.

Table 129: Number of Adverse Events Occurring in 5% of Subjects in Any Treatment Group by MedDRA System Organ Class and Preferred Term, and Treatment Group - Safety Population

Preferred Term	MedDRA System Organ Class	MedDRA Version	LACTIN-V (N=X)	Placebo (N=X)	All Subjects (N=X)
xxxxxx	xxxxxxxxxx	xx.x	xx	xx	xx
Notes: N = Number of subjects in the Safety Analysis Population					

Table 130: Subjects Reporting Adverse Events Occurring in 5% Subjects in Any Treatment Group by MedDRA System Organ Class and Preferred Term, and Treatment Group - Safety Population

Preferred Term	MedDRA System Organ Class	MedDRA Version	LACTIN-V (N=X)	Placebo (N=X)	All Subjects (N=X)
xxxxxx	xxxxxxxxxx	xx.x	xx	xx	xx

Notes: N = Number of subjects in the Safety Analysis Population

Table 131: Listing of Non-Serious, Unsolicited, Moderate or Severe Adverse Events

Adverse Event	Study Day	Severity	Relationship to Study Treatment	In Not Related, Alternative Etiology	Action Taken with Study Treatment	Subject Discontinued Due to AE	Outcome	MedDRA System Organ Class	MedDRA Preferred Term
Subject ID: , Treatment Group: , AE Number:									
xxxxxxx	xx	xxxxxx	xxxxxx	xxxxx	xxxxxx	Y/N	xxxxx	xxxxx	xxxxx
Comments:xxxxxxxxxx									
Subject ID: , Treatment Group: , AE Number:									
xxxxxxx	xx	xxxxxx	xxxxxx	xxxxx	xxxxxx	Y/N	xxxxx	xxxxx	xxxxx
Comments:xxxxxxxxxx									

Table 132: Listing of Serious Adverse Events

Adverse Event	Study Day the Event Became Serious	Reason Reported as an SAE	Severity	Relationship to Study Treatment	In Not Related, Alternative Etiology	Action Taken with Study Treatment	Subject Discontinued Due to AE	Outcome	MedDRA System Organ Class	MedDRA Preferred Term
Subject ID: , Treatment Group: , AE Number:										
xxxxxxx	xx	xxxxxx	xxxxxx	xxxxxx	xxxxxx	xxxxxx	Y/N	xxxxx	xxxxx	xxxxx
Comments: xxxxxxxxxxxxxxx										
Subject ID: , Treatment Group: , AE Number:										
xxxxxxx	xx	xxxxxx	xxxxxx	xxxxxx	xxxxxx	xxxxxx	Y/N	xxxxx	xxxxx	xxxxx
Comments: xxxxxxxxxxxxxxx										

Narratives of Deaths, Other Serious and Significant Adverse Events (not included in SAP, but will be included in the CSR)

Table 133: Abnormal Discharge and Cervical Mucus Characteristics by Visit and Treatment Group - Safety Population

All Subjects (N=X)									
Category	Value	Visit 1 (N=X)		Visit 2 (N=X)		Visit 3 (N=X)		Visit 4 (N=X)	
		n	%	n	%	n	%	n	%
Abnormal Discharge									
Source	Vagina	x	x	x	x	x	x	x	x
	Cervix/vagina	x	x	x	x	x	x	x	x
Amount	Minimal	x	x	x	x	x	x	x	x
	Moderate	x	x	x	x	x	x	x	x
	Profuse	x	x	x	x	x	x	x	x
Character	Thin/watery	x	x	x	x	x	x	x	x
	Normal	x	x	x	x	x	x	x	x
	Thicker than normal	x	x	x	x	x	x	x	x
Color	White	x	x	x	x	x	x	x	x
	Clear	x	x	x	x	x	x	x	x
	Yellow	x	x	x	x	x	x	x	x
	Brown	x	x	x	x	x	x	x	x
	Bloody	x	x	x	x	x	x	x	x
Consistency	Non-homogenous (normal)	x	x	x	x	x	x	x	x
	Homogenous	x	x	x	x	x	x	x	x
	Curdy/Plaques	x	x	x	x	x	x	x	x
	Frothy	x	x	x	x	x	x	x	x
	Other	x	x	x	x	x	x	x	x
Distribution	Pooled	x	x	x	x	x	x	x	x
	Diffuse	x	x	x	x	x	x	x	x
	Patches	x	x	x	x	x	x	x	x
Odor	None	x	x	x	x	x	x	x	x
	Foul	x	x	x	x	x	x	x	x
	Fishy	x	x	x	x	x	x	x	x
Cervical Mucus									
Amount	Minimal (to os)	x	x	x	x	x	x	x	x
	Moderate (on face)	x	x	x	x	x	x	x	x
	Profuse (pools)	x	x	x	x	x	x	x	x
Color	Clear	x	x	x	x	x	x	x	x
	Opaque White	x	x	x	x	x	x	x	x
	Translucent White	x	x	x	x	x	x	x	x
	Yellow	x	x	x	x	x	x	x	x
	Brown	x	x	x	x	x	x	x	x

All Subjects (N=X)									
Category	Value	Visit 1 (N=X)		Visit 2 (N=X)		Visit 3 (N=X)		Visit 4 (N=X)	
		n	%	n	%	n	%	n	%
	Bloody	x	x	x	x	x	x	x	x
Viscosity	Thin	x	x	x	x	x	x	x	x
	Average	x	x	x	x	x	x	x	x
	Thick	x	x	x	x	x	x	x	x

Note: Denominator for percentages are the number of subjects with abnormal discharge that can be evaluated at the respective visit

Tables with similar format:

Table 134: Abnormal Discharge and Cervical Mucus Characteristics by Visit and Treatment Group - Safety Population - LACTIN-V

Table 135: Abnormal Discharge and Cervical Mucus Characteristics by Visit and Treatment Group - Safety Population - Placebo

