7.5 Follow-Up Study Visit 4, Week 12, Day 84 (Allowable Days 77-91)

The following procedures and assessments will be performed at Visit 4, Week 12, Day 84:

1. Participants will return on Day 84. Staff will review the memory aid with the participant. The participant will be asked about symptoms, concomitant medications and any medical problems since the last visit, which will be recorded on the appropriate CRF. The participant will be asked to provide exact dates and times of the study product administration.
2. Medical, gynecological and sexual history to include assessment of STI and HIV risk

3. Symptom-directed physical and pelvic examination by a study physician or nurse that will include vital signs, including temperature, and examination of respiratory and cardiovascular systems, as well as assessment of symptoms and adverse events
4. The pelvic examination will be conducted in the following order:
 - a. Examination of the external genitalia
 - b. Speculum insertion and examination of vagina, fornices and cervix with naked eye. Water will be used to ease speculum insertion. No lubricant should be used as it could contain chlorhexidine which may kill *Lactobacillus*.
 - c. Vaginal pH
 - d. Vaginal swab for wet mount taken from the posterior fornix for yeast vaginitis and clue cells and for amine test (whiff test)
 - e. Vaginal swab for Gram stain (Nugent scoring system)
 - f. Vaginal swabs (no more than two) for storage and future identification of vaginal bacteria, and possible multiomic (e.g. proteomics, metabolomics, etc.) testing
 - g. Vaginal swabs for *L. crispatus* identification with qPCR
 - h. If indicated, cervical (or vaginal) swab for nucleic acid amplification of *N. gonorrhoeae*, *C. trachomatis*, and *T. vaginalis*
5. If indicated, clean catch urine dipstick; urinalysis if abnormal results indicate
6. If indicated, urine β hCG pregnancy test
7. All clinical and laboratory findings at the time of the evaluation will be recorded on the CRF. These findings will include observations present on the pelvic exam such as genital findings including location; presence or absence, and character of vaginal or cervical discharge or lesions; and results of any on-site tests.
8. Participants will be asked to answer a detailed self-administered questionnaire assessing the acceptability of the study product and the applicator to evaluate the possible change of attitudes over time.

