6.3. Analysis Populations

6.3.1. Safety Analyses

All safety analyses will be performed in the safety analysis population. The safety population includes all randomized subjects who received at least one dose of study product. In the unlikely event of an error in randomization or study product administration (i.e., incorrect product), subjects will be grouped by the product they actually received.

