As an additional analysis of the colonization analyses, the median time to colonization (from randomization) will be estimated by treatment group using Kaplan-Meier estimates ([Table 54](#)). In addition, the median 95% confidence interval, minimum, first quartile, third quartile, and maximum Kaplan-Meier estimates of time to BV recurrence will be presented. For subjects who experience colonization by Visit 4 (Week 12), the time of colonization will be defined as the midpoint between the earliest time point of colonization (post-baseline) and the previous observed time point. For subjects without colonization at or before Visit 4, the colonization endpoint will be coded as censored, with time to colonization defined as the elapsed time from the first dose of study product, to the Visit 4 time point, or to the first occurrence of loss to follow-up or the time-point at which the subject became ineligible for the particular analysis population. Time to colonization by Visit 7 (Week 24) will be defined similarly. Kaplan-Meier curves for colonization will also be generated ([Figure 4](#) and [Figure 5](#)).

[Table 55](#) will present the proportion of subjects who were compliant (See Section 3.3.5) with the dose regimen through their first BV recurrence or through Visit 4 (Week 12) (and 95% Wilson confidence interval) in each treatment group with difference in compliance proportions between treatment groups (and 95% Wilson confidence interval). The summaries will be presented in the ITT, mITT, and CC populations. The p-value from the Chi-Square test will also be presented. [Table 56](#), [Table 57](#), [Table 58](#), [Table 59](#), [Table 60](#), [Table 61](#), and [Table 62](#) will present summaries of product administration via subject report, returned applicators, and staining for each week. Summaries will be presented by clinical site and treatment group. [Listing 7](#) and [Listing 8](#) will present individual dosing data.

The responses to the acceptability questionnaire at screening and at Visit 4 (Week 12) will be summarized by treatment group. For categorical responses, the proportion of subjects with the particular response and its associated 95% Wilson confidence interval will be used ([Table 63](#) and [Table 64](#)). For continuous or discrete responses, the mean, standard deviation, median, and range of responses will be used ([Table 65](#) and [Table 66](#)).

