The analyses will be performed in the ITT, mITT, CC, and PP populations. Individual responses will be included in [Listing 9](#).

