		Number of Subjects with Response n	Number of Subjects Queried N	Proportion of Subjects with Response	Response 95% CI ¹	Number of Subjects with Response n	Number of Subjects Queried N	Proportion of Subjects with Response	Response 95% CI ¹
How many episodes of BV have you experienced in your life?	None	x	x	0.xx	0.xx, 0.xx	x	x	0.xx	0.xx, 0.xx
	1-2	x	x	0.xx	0.xx, 0.xx	x	x	0.xx	0.xx, 0.xx
	3-4	x	x	0.xx	0.xx, 0.xx	x	x	0.xx	0.xx, 0.xx
	5 or more	x	x	0.xx	0.xx, 0.xx	x	x	0.xx	0.xx, 0.xx
	Unknown	x	x	0.xx	0.xx, 0.xx	x	x	0.xx	0.xx, 0.xx
If you have had BV in the past, what have you used for treatment?	Nothing	x	x	0.xx	0.xx, 0.xx	x	x	0.xx	0.xx, 0.xx
	Antibiotics	x	x	0.xx	0.xx, 0.xx	x	x	0.xx	0.xx, 0.xx
	Probiotics	x	x	0.xx	0.xx, 0.xx	x	x	0.xx	0.xx, 0.xx
	Home remedies	x	x	0.xx	0.xx, 0.xx	x	x	0.xx	0.xx, 0.xx
	Other	x	x	0.xx	0.xx, 0.xx	x	x	0.xx	0.xx, 0.xx
Unknown	x	x	0.xx	0.xx, 0.xx	x	x	0.xx	0.xx, 0.xx	
If you ever had BV and treated it, how would you reply to the following statement: “I believe the treatment I have previously used are effective in treating BV”.	Strongly Agree	x	x	0.xx	0.xx, 0.xx	x	x	0.xx	0.xx, 0.xx
	Agree	x	x	0.xx	0.xx, 0.xx	x	x	0.xx	0.xx, 0.xx
	Neutral	x	x	0.xx	0.xx, 0.xx	x	x	0.xx	0.xx, 0.xx
	Disagree	x	x	0.xx	0.xx, 0.xx	x	x	0.xx	0.xx, 0.xx
	Strongly Disagree	x	x	0.xx	0.xx, 0.xx	x	x	0.xx	0.xx, 0.xx
Etc.									
Notes: Denominator of percentages is the number of subjects in the Safety Population in the respective treatment group 1: 95% CI= 95% Wilson confidence interval									

Tables with similar format:

Table 64: Categorical Responses to Acceptability Questionnaire by Treatment Group –Visit 4 (Week 12)

Table 65: Continuous/Discrete Responses to Acceptability Questionnaire by Treatment Group – Screening Visit

Questionnaire Item	Questionnaire Sub-Item	LACTIN-V (N = x)			Placebo (N = x)		
		Mean (SD)	Median	Range	Mean (SD)	Median	Range
On a scale of 0 to 10, with 0 being “not at all bothersome” to 10 being “extremely bothersome”, I found the following symptoms of BV:	Increase vaginal discharge	xx.x (xx.xx)	xx.xx	xx.x, xx.x	xx.x (xx.xx)	xx.xx	xx.x, xx.x
	Vaginal odor	xx.x (xx.xx)	xx.xx	xx.x, xx.x	xx.x (xx.xx)	xx.xx	xx.x, xx.x
	Vaginal irritation and itching	xx.x (xx.xx)	xx.xx	xx.x, xx.x	xx.x (xx.xx)	xx.xx	xx.x, xx.x
	Pain with urination	xx.x (xx.xx)	xx.xx	xx.x, xx.x	xx.x (xx.xx)	xx.xx	xx.x, xx.x
	Other	xx.x (xx.xx)	xx.xx	xx.x, xx.x	xx.x (xx.xx)	xx.xx	xx.x, xx.x

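### The Table 63–64 footnote, its own N column and SAP 8.2 disagree on the denominator and population for questionnaire responses; applying the footnote at Week 12 would scale every proportion by that arm's response rate

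*SAP*

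**What the plan says.** SAP 8.2 plans the questionnaire summaries at two times: "The responses to the acceptability questionnaire at screening and at Visit 4 (Week 12) will be summarized by treatment group". For categorical items, "the proportion of subjects with the particular response and its associated 95% Wilson confidence interval will be used". The section closes this topic with "The analyses will be performed in the ITT, mITT, CC, and PP populations".

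The shell for categorical items is Table 63 (screening) in SAP Appendix 1. Table 64 (Visit 4, Week 12) is listed as having a similar format and so takes the same layout and footnote. Within each arm the shell has a header N and, on each row, n, a column headed "Number of Subjects Queried N", the proportion and its interval. The footnote reads "Denominator of percentages is the number of subjects in the Safety Population in the respective treatment group". There are no rows for analysis populations.

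SAP 6.3.1 defines the set named in the footnote: "The safety population includes all randomized subjects who received at least one dose of study product". Protocol 7.5 fixes when the Week 12 answers are collected, at Visit 4: "Participants will be asked to answer a detailed self-administered questionnaire assessing the acceptability of the study product and the applicator". Protocol 7.9 also gives the questionnaire at product discontinuation or early termination, but SAP 8.2 summarises only screening and Visit 4. The missing-data section (SAP 6.5) covers recurrence and colonization and does not mention the questionnaire.

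**The concern.** A programmer has two competing denominators in one shell, the Safety N and the number queried, and the text names populations that match neither label. Two programmers could report different percentages from the same data.

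The footnote is the explicit rule, and at Week 12 it has a consequence. A dosed woman who never reaches Visit 4, or attends and leaves an item blank, stays in the denominator and counts as not having given any of the listed answers. Each arm's proportions then mix what women answered with how many answered. Acceptability belongs to Secondary Objective 2 and is read arm against arm, so a difference in non-response could be taken for a difference in opinion.

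At screening the footnote causes a different problem. The five-level agreement item on whether earlier BV treatment worked is put only to women who have had BV and treated it. A Safety denominator divides it by women to whom it does not apply, and the shell shows no row for them.

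**Working it through.** **Side by side**

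| Source | What it implies |
|---|---|
| Table 63 footnote (also Table 64) | Safety population, per arm |
| Table 63 N column | Women queried |
| SAP 8.2 | ITT, mITT, CC and PP; no rule for non-responders |
| Tables 13, 23, 31 and 35 (by-visit recurrence, colonization, sex acts, partners) | Women in the population with data at that visit |
| Tables 109–112 (solicited events) | Safety subjects with solicited-event data |

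The last two rows show that the SAP limits the denominator to women with data in comparable displays.

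**Arm sizes.** The documents give no figure for acceptability. The planned total of 228 (SAP 5) supplies arm sizes. It reproduces with 30% against 15%, two-sided 5%, 70% power, 2:1 and a pooled-variance chi-square formula:

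- Pooled proportion (0.30 + 2 × 0.15)/3 = 0.20.
- n(placebo) = [1.960 × √(1.5 × 0.20 × 0.80) + 0.524 × √(0.30 × 0.70 + 0.15 × 0.85/2)]² / 0.15² = 67.7, so 68, and 204 in total.
- With 10% drop-out: 204/0.9 = 226.7, so 227; rounding by arm, 68/0.9 = 75.6, so 76, and 3 × 76 = 228.

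The illustration uses 152 LACTIN-V and 76 placebo, all dosed.

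**Effect of the footnote.** Proportion shown = proportion among responders × (responders / Safety N).

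Assumed inputs: 79% favourable among responders, borrowed from the Phase II-a result in Protocol 2.1 (19 of 24), and Week 12 non-response of 5% to 20%. The 10% row borrows the SAP's drop-out assumption for the CC population, which is not a questionnaire response rate. LACTIN-V arm:

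| Non-response | Answered | Favourable | Among responders | On Safety N (152) |
|---|---|---|---|---|
| 5% | 144 | 114 | 79% | 75% |
| 10% | 137 | 108 | 79% | 71% |
| 15% | 129 | 102 | 79% | 67% |
| 20% | 122 | 96 | 79% | 63% |

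At 10%, the Wilson 95% interval is 71.3% to 84.8% for 108/137 and 63.4% to 77.7% for 108/152.

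The other answers shrink too. At 10%, the 137 − 108 = 29 remaining women go from 29/137 = 21% to 29/152 = 19%. The two groups together reach 137/152 = 90%; the missing 10% is the non-response.

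**Unequal non-response, equal opinion.** With 5% non-response on LACTIN-V and 20% on placebo, 114/144 = 79% and 48/61 = 79% are shown as 114/152 = 75% and 48/76 = 63%, a gap of 12 points. With 8% and 15%, 0.79 × 0.92 = 73% and 0.79 × 0.85 = 67%. These pairs of rates are also assumptions.

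**The case against.** The strongest reply is that the footnote is only misworded. A row-level N is redundant if every proportion uses the arm's Safety N. The companion shell for continuous items, Table 65, has only a header N and labels that N as Safety. So the Safety label in Table 63 may be meant for the header, with the proportion taken over women queried. This is plausible, and in that case women who were not asked drop out. It does not settle the matter, because the footnote refers to the denominator of percentages and nothing in the SAP says which statement governs.

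Several stronger readings are tempting and are not supported:

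- **That the plan understates Week 12 acceptability.** This depends on the footnote being used. Unfavourable answers shrink as well. Nor is the responders' figure necessarily the true one: in Phase II-a, women with persistent symptomatic BV were less satisfied (Protocol 2.1), so if such women are less likely to answer, a responders-only proportion could be too high.
- **That there are three denominators.** SAP 8.2 names populations and does not say how non-responders count within them. There are two competing denominators and a separate population mismatch.
- **That categories should always sum to 1.** Listing 9 gives item 2 six yes/no sub-items, matching the six options of the past-treatment item, so that item appears to allow several answers. The argument holds for single-choice items.
- **That conditional items distort the Week 12 results.** The conditional items shown are in the screening table, and no Week 12 item is displayed.

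It is also fair to say that no test is planned for these responses, that the shell prints n and N, and that Listing 9 gives individual answers, so a reader could recompute.

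**Conclusion.** The point stands as a contradiction in the SAP with a conditional consequence. The footnote conflicts with the N column in its own shell and with the populations in SAP 8.2. If it is applied at Week 12, each proportion is scaled by its arm's response rate and the Wilson interval rests on the wrong N; at screening, the single-choice conditional item is also divided by women it does not concern.

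The size is unknown because the documents give no Week 12 response rate. The drop from 79% to between 75% and 63% rests on an assumed favourable level and assumed non-response. Means in Tables 65–66 are not diluted in this way. The matter is minor: one descriptive secondary outcome is affected and the primary analysis is not. It is still worth correcting, since the written rule departs from the SAP's own practice in comparable displays.

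**What to change.** Three edits, best made before unblinding:

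1. Reword the Table 63–64 footnote so that the denominator is the number of women in the stated analysis population with a response to the item and, for conditional items, to whom it applies. Make the N column heading agree. A queried count alone would still include women who were asked and did not answer.
2. Add a line showing, by arm, how many women did not answer, so that unequal non-response is visible.
3. Reconcile the population: either add ITT, mITT, CC and PP rows to the shells, or amend SAP 8.2 to name the population actually used. Naming a population does not replace the first edit. ITT keeps women with no Visit 4 questionnaire, and so can CC, which admits women followed only to a first BV diagnosis.

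The cost is a small amount of shell or text editing, more if population rows are added. No new data are needed.
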